2 STUDY OBJECTIVES

2.1 Primary Objectives

Safety

- Proportion of subjects without any localized or systemic safety events through 30 days that affect the access or venous outflow circuit and resulted in surgery, hospitalization, or death
 - Safety events in this calculation will not include venous outflow obstructions, which are captured in the calculation of Assisted Primary Patency of the target lesion, Assisted Primary Patency of the venous outflow circuit and Index of Patency Function

Effectiveness

- Proportion of subjects with Target Lesion Primary Patency at 30 days
 - Time to loss of Target Lesion Primary Patency is defined as the time interval of uninterrupted patency from initial study procedure to the next intervention performed on the target lesion or uncorrectable target lesion occlusion, whichever occurs first

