2.2 Secondary Objectives

- Proportion of subjects with Target Lesion Primary Patency at 3, 6 and 12 months
- Proportion of subjects with Assisted Primary Patency of the target lesion at 30 days, 3, 6 and 12 months
 - Time to loss of Assisted Primary Patency of the target lesion is defined as time following study procedure until uncorrectable target lesion occlusion
- Proportion of subjects with Primary Patency of the venous outflow circuit at 30 days, 3, 6, and 12months
 - Time to loss of Primary Patency of the venous outflow circuit is defined as the time following initial study procedure until the next venous outflow circuit intervention
- Proportion of subjects with Assisted Primary Patency of the venous outflow circuit at 30 days, 3, 6 and 12 months.

- Time to loss of Assisted Primary Patency of the venous outflow circuit is defined as the time following initial study procedure until complete access abandonment.
- Index of Patency Function at 3, 6 and 12 months, defined as time from initial study procedure to complete access abandonment divided by number of venous outflow circuit re-interventions to maintain hemodialysis
- Procedure or device related adverse events at 3, 6 and 12 months
- Clinical Success
 - The resumption of successful dialysis through existing access for at least one session following initial study procedure
- Anatomic Success
 - Less than 30% residual stenosis immediately following study procedure
- Procedural Success
 - The achievement of both clinical and anatomic success

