5 TREATMENT AND ASSESSMENT

Delivery of the WRAPSODY stent graft will be according to the procedure in Appendix B.

Visit Schedule

Visit 1:

- Screening
 - Informed consent
 - Eligibility criteria assessment
 - Demographics
 - Vital Signs
 - Medical History relevant to dialysis:
 - Type, location and date of all previous venous outflow circuit intervention(s)
 - Prior dialysis access type(s)
 - Location of current dialysis access (AVF/AVG)
 - For subjects with AV fistula, date fistula was first used for dialysis
 - For subject with AV graft, date of graft creation
 - Clinical reason(s) subject was referred for obstruction evaluation
 - Targeted physical exam, including at a minimum the following Clinical Indicators of Obstruction:
 - Assessment of edema in hand, arm, neck, head or trunk
 - Pain related to dialysis circuit
 - Respiratory symptoms
 - Neurological symptoms
 - Skin changes
 - Concurrent medical conditions
 - Concomitant medications

- Serum pregnancy test, if applicable
- Angiographic Imaging with location, length and percent stenosis of target lesion
- Doppler ultrasound to be performed prior to procedure
 - NOTE: A doppler ultrasound must be attempted for each subject prior to the study procedure. However, if doppler ultrasound results are unobtainable in some cases due to lesion location, this will not be considered a protocol violation.
- Study procedure (WRAPSODY Stent Graft Placement)
 - Length and diameter of stent graft
 - Percent residual stenosis
 - Doppler ultrasound post stent graft placement
 - NOTE: A doppler ultrasound must be attempted for each subject after the study procedure. However, if doppler ultrasound results are unobtainable in some cases due to lesion location, this will not be considered a protocol violation.
 - Adverse event review
 - Investigator's assessment of technical success (defined as successful deployment at intended location)
 - Procedural medications

Visit 2: 30 days (\pm 7 days)

- Targeted physical exam, including at a minimum the following Clinical Indicators of Obstruction:
 - Assessment of edema in hand, arm, neck, head or trunk
 - Pain related to dialysis circuit
 - Respiratory symptoms
 - Neurological symptoms
 - Skin changes
- Hemodialysis adequacy at the first session following the study procedure
- Adverse event review
- Interventions on venous outflow circuit since last visit
- Concomitant medications

Visit 3: 3 months (± 4 weeks)

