- Targeted physical exam, including at a minimum the following Clinical Indicators of Obstruction:
 - Assessment of edema in hand, arm, neck, head or trunk
 - Pain related to dialysis circuit
 - Respiratory symptoms
 - Neurological symptoms
 - Skin changes
- Adverse event review
- Interventions on venous outflow circuit since last visit
- Concomitant medications

Visit 4: 6 months (± 4 weeks)

- Targeted physical exam, including at a minimum the following Clinical Indicators of Obstruction:
 - Assessment of edema in hand, arm, neck, head or trunk
 - Pain related to dialysis circuit
 - Respiratory symptoms
 - Neurological symptoms
 - Skin changes
- Adverse event review
- Interventions on venous outflow circuit since last visit
- Concomitant medications

Visit 5: 12 months (± 8 weeks)

Traditional visit windows are being expanded for the 12-month visit to allow for potential impacts due to COVID-19.

- Targeted physical exam, including at a minimum the following Clinical Indicators of Obstruction:
 - Assessment of edema in hand, arm, neck, head or trunk
 - Pain related to dialysis circuit
 - Respiratory symptoms
 - Neurological symptoms
 - Skin changes
- Adverse event review
- Interventions on venous outflow circuit since last visit

- Concomitant medications
- X-rays of the treated area (subset of subjects with thoracic central venous target lesions only)
 - Minimum of two projections required to visualize WRAPSODY stent graft

Additional visits, as needed/referred for evaluation/treatment of venous outflow dysfunction

- Angiographic Evaluation, if medically indicated
- Clinical reason(s) subject was referred for obstruction evaluation
- Targeted physical exam, including at a minimum the following Clinical Indicators of Obstruction:
 - Assessment of edema in hand, arm, neck, head or trunk
 - Pain related to dialysis circuit
 - Respiratory symptoms
 - Neurological symptoms
 - Skin changes
- Interventions on venous outflow circuit since last visit
- Adverse event review
- Current intervention, if done, including:
 - Procedure type
 - Lesion location and length
 - % stenosis before treatment
 - % residual stenosis after treatment
- Concomitant medications
- X-rays of the treated area (subset of subjects with thoracic central venous target lesions only)
 - Subjects who were unable to have X-Rays completed at scheduled Visit 5 (12 Months) may be brought back for an additional visit to complete X-Rays after obtaining proper consent.

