9 STATISTICAL ANALYSIS

Analysis Sets

Safety Population: The safety population will include all enrolled subjects who received the treatment.

Efficacy Population: The efficacy population will include all enrolled subjects who received the treatment as specified in the protocol and met all eligibility criteria.

The primary safety endpoint is the proportion of subjects without any localized or systemic safety event through 30 days that affect the venous access circuit and resulted in surgery, hospitalization, or death. Safety events in this calculation will not include venous outflow obstructions which are captured in the calculation of assisted primary patency of the target lesion, assisted primary patency of the venous outflow circuit, and index of patency function. This is an observational study, and outcomes will be summarized, but no comparisons will be performed. Confidence intervals will be provided for all outcome calculations wherever possible.

The primary effectiveness endpoint is the proportion of subjects with target lesion Primary Patency at 30 days. Time to loss of target lesion Primary Patency is defined as the time interval of uninterrupted patency from initial study procedure to the next intervention performed on the target lesion or uncorrectable target lesion occlusion, whichever occurs first.

Sample Size

A sample size of approximately 50 subjects was chosen as appropriate for an initial safety and efficacy evaluation.

The primary effectiveness analyses of target lesion Primary Patency at 30 days will be summarized using number and proportion of subjects with Target Lesion Primary Patency at that timepoint.

This methodology will be repeated to test secondary endpoints, proportion of subjects with: target lesion Primary Patency at 3, 6, and 12 months; Assisted Primary Patency of target lesion at 3, 6, and 12 months; Primary Patency of the venous outflow circuit at 3, 6, and 12 months; Assisted Primary Patency of the venous outflow circuit at 3, 6, and 12 months.

The primary safety endpoint will be summarized using number and proportion of subjects without any localized or systemic safety event that affected the access or venous outflow circuit and resulted in surgery or hospitalization or death through 30 days.

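### A documented but correctable target lesion occlusion that is still untreated at day 30 counts as patent in the primary effectiveness endpoint

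*Combined protocol and SAP*

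**What the plan says.** Section 2.1 names the primary effectiveness endpoint as "Proportion of subjects with Target Lesion Primary Patency at 30 days" and defines the underlying time as the interval of "uninterrupted patency from initial study procedure to the next intervention performed on the target lesion or uncorrectable target lesion occlusion, whichever occurs first". Section 4 repeats this in substance. Section 9 also ends the interval at "the next intervention performed on the target lesion or uncorrectable target lesion occlusion, whichever occurs first" and adds no rule for other occlusions, thrombosis or bypass. None of the three sections says what makes an occlusion uncorrectable, who decides, or which date applies.

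Section 2.2 puts the same qualifier into the assisted measure: "Time to loss of Assisted Primary Patency of the target lesion is defined as time following study procedure until uncorrectable target lesion occlusion".

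For ascertainment around day 30, Visit 2 in Section 5 has a targeted physical exam, a review of interventions, and "Hemodialysis adequacy at the first session following the study procedure". It has no imaging of the target lesion. Additional visits allow "Angiographic Evaluation, if medically indicated". Section 8 has the DMC/CEC adjudicate target lesion and access circuit interventions.

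Sections 2.1, 4 and 9 leave venous outflow obstructions out of the primary safety endpoint, and Section 7.1 does not count them as adverse events. The reason given is that the two assisted patency measures and the Index of Patency Function capture them.

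**The concern.** The definition opens with uninterrupted patency but closes on events that need not coincide with its interruption. Loss is dated when someone treats the lesion, or when the occlusion is judged beyond correction, and not when the lesion is found occluded. An occlusion that is known, correctable and not yet treated meets neither condition.

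At stake is the primary effectiveness figure of a single-arm, first-in-human study. The rule can only omit a loss or date it late, so any error raises the patency rate, and there is no control arm in which the same error would also occur. It falls on complete occlusions, which are among the clearest device failures. Because obstructions are also removed from safety, such a subject can count as a failure in neither primary endpoint.

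**Working it through.** **No planned figure to reproduce.** Section 9 gives about 50 subjects without a calculation, target rate or performance goal. The check is therefore a reading of the definition, followed by arithmetic for scale.

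**Step 1: apply the rule to illustrative cases.**

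| Case | End event as written | Status at day 30 |
|---|---|---|
| Occlusion documented day 26, reopened day 32 | Intervention, day 32 | Patent |
| Occlusion documented day 20, target lesion intervention day 35 | Intervention, day 35 | Patent |
| Correctable occlusion documented by day 30, never treated, subject still in study | None | Patent |
| Bypass before day 30, lesion left in place | Not literally on the target lesion | Depends on DMC/CEC |
| Occlusion declotted before day 30 | Intervention, on that day | Lost |
| Access abandoned before day 30 | Subject withdrawn (Section 6) | No rule given |

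The first three rows are the problem. The fourth is uncertain, the fifth is scored correctly, and the sixth is a gap.

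**Step 2: look for another place that catches the first three.** Visit 2 has no lesion imaging, and its dialysis item concerns only the first session after the procedure. The DMC/CEC remit in Section 8 lists interventions, not untreated occlusions. Adverse event reporting excludes obstructions. Of the measures said to capture them, target lesion assisted patency needs an uncorrectable occlusion, circuit assisted patency needs complete abandonment, and the Index of Patency Function counts re-interventions. A correctable occlusion untreated at day 30 is in none of these at that date.

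**Step 3: value of one subject.** 1/50 = 2.0 percentage points. Starting from 50/50, with exact (Clopper-Pearson) 95% intervals, an assumed method because Section 9 names none:

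| Reclassified | Rate | 95% CI |
|---|---|---|
| 0 | 100.0% | 92.9–100.0 |
| 1 | 98.0% | 89.4–99.9 |
| 2 | 96.0% | 86.3–99.5 |
| 3 | 94.0% | 83.5–98.7 |

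The chance of at least one such subject is 1 − (1 − p)^50. For assumed true rates p of 1%, 2% and 5% it is 39.5%, 63.6% and 92.3%. The documents give no value for p.

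**Step 4: how many from delayed treatment alone.** The inputs are the stent-graft patency figures cited in Sections 1.2 and 1.3. Assumptions: constant hazard, every loss starting as an occlusion, and treatment L = 7 or 14 days later.

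- h = −ln(S)/t, with 6 months = 182.5 days and 3 months = 91 days
- losses by day 30 = 50 × (1 − S(30))
- losses with onset in the last L days = 50 × (S(30 − L) − S(30))

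For 51.6% at 6 months: h = 0.6616/182.5 = 0.00363 per day, S(30) = 0.897, S(23) = 0.920, and 50 × (0.920 − 0.897) = 1.15.

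| Cited patency | Losses by day 30 | Scored patent, L = 7 | Scored patent, L = 14 |
|---|---|---|---|
| 51.6% at 6 months | 5.15 | 1.15 | 2.34 |
| 66.4% at 6 months | 3.25 | 0.74 | 1.49 |
| 97% at 3 months | 0.50 | 0.12 | 0.23 |

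At 2 points per subject this runs from about 0.2 points (0.12 × 2) to 4.7 points (2.34 × 2). Given the hazard and the lag, these are upper bounds for the delayed-treatment route, because not every loss begins as an occlusion. They do not cover occlusions never treated, or bypasses.

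**The case against.** The strongest reply is that uninterrupted patency is part of the definition, so an adjudicator could treat any occlusion as a loss. That reading makes the qualifier uncorrectable redundant, and the sentence names the two events to which the interval runs. At best two analysts could score the same subject differently, which needs fixing too.

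Ascertainment is also fuller than imaging alone. Visit 2 includes an exam for clinical indicators of obstruction, dysfunction can lead to an additional visit with angiography, and Section 12 has sites ask dialysis centers about revisions done elsewhere. This stands, but it helps an occlusion become known. It does not change how a known one is scored.

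The size is soft, and this stands in full. Section 1.2 describes the 51.6% and 66.4% studies as in-stent stenosis or restenosis, and the former also included thrombotic access. Exclusions 5f and 20 bar both conditions. The remaining input gives 0.1 to 0.2 subjects. The lags have no support in the documents. Section 9 plans no comparisons, so no test or pass/fail decision turns on one or two subjects.

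Four stronger inferences should be resisted:

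- **Repeated declotting preserves Primary Patency.** It does not. The first declotting of the target lesion is an intervention and ends it. Only the assisted measure continues.
- **Abandonment is scored a success.** Section 6 withdraws the subject. The documents do not say how 30-day patency is then scored.
- **A bypass is certainly scored a success.** Section 8 sends access circuit interventions to the DMC/CEC, which may class it as a loss.
- **Assisted patency is overstated beside the central-vein figures in Section 1.3.** The cited study's definition is not given, so this cannot be judged.

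**Conclusion.** The point holds for documented, correctable occlusions untreated at day 30: under the rule in Sections 2.1, 4 and 9 they are scored patent, and nothing else in the plan corrects this. For bypass it holds only as a possibility. The direction is certain and the size is not. Each subject is worth 2 points at n=50, and the expected number cannot be derived from the documents. Under the assumptions shown, delayed treatment alone accounts for well under one to about two subjects, and the input not drawn from an in-stent population sits at the low end.

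The same qualifier in Section 2.2 means target lesion assisted patency does not count a correctable occlusion, so the reason given for excluding obstructions from safety fails for these cases. This is a change that should be made to the primary effectiveness endpoint. It is not evidence that the reported rate will be materially biased.

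**What to change.** - **Sections 2.1, 4 and 9:** end Target Lesion Primary Patency at the earliest of (i) any intervention on the target lesion, (ii) any documented target lesion occlusion or thrombosis, correctable or not, dated at the best documented onset and otherwise at first documentation, or (iii) a surgical bypass or revision that excludes the target lesion.
- **Data capture and Section 8:** add an occlusion-date field, and send documented occlusions to the DMC/CEC together with the interventions.
- **Section 9:** state how access abandonment before day 30 is scored.
- **Section 2.2:** report time to first documented target lesion occlusion beside the current assisted measure, and define uncorrectable and who decides it. Renaming the current measure is optional.

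The cost is wording in four sections, one data field, a somewhat wider adjudication remit, one added derived endpoint and a slightly less favorable patency figure. Interventions, referral reasons and any angiograms are already collected. The change will not detect silent occlusions, and an occlusion first documented after day 30 with no onset date would still be scored patent at day 30.

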2.2 Secondary Objectives

- Proportion of subjects with Target Lesion Primary Patency at 3, 6 and 12 months
- Proportion of subjects with Assisted Primary Patency of the target lesion at 30 days, 3, 6 and 12 months
 - Time to loss of Assisted Primary Patency of the target lesion is defined as time following study procedure until uncorrectable target lesion occlusion
- Proportion of subjects with Primary Patency of the venous outflow circuit at 30 days, 3, 6, and 12months
 - Time to loss of Primary Patency of the venous outflow circuit is defined as the time following initial study procedure until the next venous outflow circuit intervention
- Proportion of subjects with Assisted Primary Patency of the venous outflow circuit at 30 days, 3, 6 and 12 months.

- Time to loss of Assisted Primary Patency of the venous outflow circuit is defined as the time following initial study procedure until complete access abandonment.
- Index of Patency Function at 3, 6 and 12 months, defined as time from initial study procedure to complete access abandonment divided by number of venous outflow circuit re-interventions to maintain hemodialysis
- Procedure or device related adverse events at 3, 6 and 12 months
- Clinical Success
 - The resumption of successful dialysis through existing access for at least one session following initial study procedure
- Anatomic Success
 - Less than 30% residual stenosis immediately following study procedure
- Procedural Success
 - The achievement of both clinical and anatomic success

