Stent grafts have been used to treat TCVO, but most reports cite their use within larger randomized clinical trials or in small cohort studies. In a study by Jones and colleagues, VIABAHN stent grafts were placed in the central veins of 42 subjects with stenosis that did not respond to PTA. Primary patency rates at 3, 6, 12, and 24 months were 97%, 81%, 67%, and 45%, respectively. Primary assisted patency rates at 3, 6, 12, and 24 months were 100%, 100%, 80%, and 75%. This suggests that stent grafts placed

for the treatment of central venous stenosis are an effective way to maintain luminal patency if PTA fails (Jones 2011).

As further support, in the RESCUE study summarized earlier, a subset of 73 subjects (total study n = 275) with stenoses in the central vein (n=41), subclavian vein (n=30), brachiocephalic vein (n=1), and superior vena cava (n=1) demonstrated statistically significantly better primary patency in the treatment area at 24 months for the stent graft group vs PTA (13.6% vs 4.3%, p < .001).

To date there have been no large prospective randomized studies to investigate stent graft performance in the central veins.

Stent grafts used in central veins are the GORE VIABAHN, FLUENCY PLUS and the FLAIR Endovascular Stent Graft. Per these products' Instructions for Use, the VIABAHN stent graft is a flexible, self-expanding endoluminal endoprostheses consisting of an expanded polytetrafluoroethylene (ePTFE) lining with an external nitinol support extending along its entire length. The FLUENCY PLUS is a flexible self-expanding vascular prosthesis comprising ePTFE encapsulating a nitinol frame work, except for 2 mm at each of the flared stent graft ends with 4 radiopaque Tantulum markers. The inner lumen of the stent graft surface is carbon impregnated. The FLAIR Endovascular Stent Graft is a flexible, self-expanding endoprostheses comprising an expanded (ePTFE) encapsulating a nitinol stent framework. The nitinol stent, including distal and proximal ends, is encapsulated within the ePTFE and the inner lumen of the stent graft is carbon impregnated. The ePTFE outer wall of the stent graft, which contacts the AV access graft and native vein, contains cutouts which expose the nitinol stent.

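### Target-lesion Assisted Primary Patency ends only at an uncorrectable occlusion, so it is cumulative patency: reopened occlusions lower neither assisted measure, although the plan says obstructions left out of safety are captured there

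*Combined protocol and SAP*

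**What the plan says.** Section 2.2 lists as a secondary objective "Proportion of subjects with Assisted Primary Patency of the target lesion at 30 days, 3, 6 and 12 months" and defines its loss: "Time to loss of Assisted Primary Patency of the target lesion is defined as time following study procedure until uncorrectable target lesion occlusion". Nothing else in the document adds first occlusion, thrombosis or a limit on repeat procedures as a loss event. Section 9 repeats the endpoint's name without a definition.

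The neighbouring endpoints are:

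- Target Lesion Primary Patency (Section 2.1) runs "to the next intervention performed on the target lesion or uncorrectable target lesion occlusion, whichever occurs first".
- The circuit version of the assisted measure (Section 2.2): "Time to loss of Assisted Primary Patency of the venous outflow circuit is defined as the time following initial study procedure until complete access abandonment".
- The Index of Patency Function (Section 2.2) is time to access abandonment "divided by number of venous outflow circuit re-interventions to maintain hemodialysis". It is reported at 3, 6 and 12 months, not at 30 days.

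Sections 2.1, 4 and 9 leave venous outflow obstructions out of the primary safety endpoint, and Section 7.1 leaves them out of adverse events. The reason given is that the two Assisted Primary Patency measures and the Index capture them.

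**The concern.** An assisted measure is useful if it tells a reader how often a lesion stayed open with help, as distinct from how often it closed and was rescued. The definition here does not draw that line. A restenosis dilated while the lesion was still open and a complete occlusion that was recanalised receive the same score.

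Two things are at stake. First, four secondary results (30 days, 3, 6 and 12 months) carry a name that a reader may take to mean patency without occlusion, when they measure freedom from irreversible occlusion. Second, the plan relies on these measures to account for obstructions it has removed from safety. If a reopened occlusion moves neither assisted measure, that account has a gap.

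**Working it through.** The documents state no expected rate or precision for this endpoint, so there is no figure to reproduce. The check is a comparison of definitions, followed by a count-based illustration.

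**Step 1. Score hypothetical records under the written rules.**

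| Record | Target Lesion Primary Patency | Assisted, as written | If lost at first complete occlusion | Re-interventions counted in the Index |
|---|---|---|---|---|
| A: 60% restenosis dilated at day 90, never closed | lost, day 90 | kept | kept | 1 |
| B1: complete occlusion at day 90, reopened | lost, day 90 | kept | lost, day 90 | 1 |
| B2: as B1, closed and reopened again at day 200 | lost, day 90 | kept | lost, day 90 | 2 |
| C: occlusion at day 90 that cannot be reopened | lost, day 90 | lost, day 90 | lost, day 90 | depends on attempts made |

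A and B1 agree on every patency endpoint in the plan and on the Index count. B2 differs from A in the Index, but only as two dilatations of an open lesion would.

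**Step 2. Apply the rules at 30 days.** Take a complete occlusion at day 20 that is reopened, with the access still in use.

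- Primary safety endpoint: not counted, because it is an obstruction (Sections 2.1, 4, 9).
- Adverse event: not counted (Section 7.1).
- Target-lesion Assisted Primary Patency: kept, because the occlusion was correctable.
- Circuit Assisted Primary Patency: kept, because the access was not abandoned.
- Index of Patency Function: not reported until 3 months.
- Primary patency of the target lesion and of the circuit: lost, exactly as after dilating an open stenosis.

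Of the three measures named as capturing obstructions, none registers this event at 30 days. In addition, Section 9 lists the assisted measures only at 3, 6 and 12 months, whereas Section 2.2 includes 30 days.

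**Step 3. Direction.** Let T_F be the time to first complete occlusion and T_U the time to uncorrectable occlusion. An uncorrectable occlusion is itself an occlusion, so T_F ≤ T_U for every subject. Hence P(T_U > t) ≥ P(T_F > t): the figure as written is never the lower of the two.

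**Step 4. Size.** With complete follow-up, gap = k/n, where k is the number of subjects with at least one reopened occlusion and no uncorrectable one by time t. With n = 50 (Section 9), each such subject is worth 1/50 = 2 points. The documents give no k, so a range is assumed. With no uncorrectable occlusion, the result as written is always 50/50 = 100% (exact 95% CI 92.9 to 100; lower limit 0.025^(1/50) = 0.929). The first-occlusion result is (50 − k)/50, with Clopper-Pearson limits:

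| k (assumed) | First-occlusion patency | Exact 95% CI | Gap |
|---|---|---|---|
| 0 | 50/50 = 100% | 92.9 to 100 | 0 |
| 1 | 49/50 = 98% | 89.4 to 99.9 | 2 points |
| 3 | 47/50 = 94% | 83.5 to 98.7 | 6 points |
| 5 | 45/50 = 90% | 78.2 to 96.7 | 10 points |

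**The case against.** The definitions are explicit and follow a pattern. Primary Patency already names uncorrectable occlusion as one of its two loss events; remove the intervention clause and the assisted definition is what remains. The circuit endpoints have a similar two-tier structure. The documents neither give nor cite a first-occlusion definition, so the plan would report exactly what it defines. All of this stands, and it makes the point one of labelling and missing information, not of miscalculation.

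Three stronger readings are tempting, and the documents do not support them.

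- *The results would be biased upward against published rates.* Section 1.3 cites primary assisted patency of 100%, 100%, 80% and 75% at 3, 6, 12 and 24 months for a central-vein stent-graft cohort. It gives no definition, so that cohort may have used either rule. Section 9 says that no comparisons will be performed.
- *Reopened occlusions disappear from the trial.* They do not. Each reopening is an intervention that ends target-lesion and circuit Primary Patency and adds to the Index count.
- *The overstatement can be put at so many points.* Multiplying cited rates of lost primary patency by an assumed share of reopened occlusions only restates the assumption. The documents contain no such share.

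Data capture is also a fair worry. Scheduled follow-up visits include no patency imaging, and angiography at additional visits is done only if medically indicated (Section 5, Appendix A). For revisions elsewhere, Section 12 has the site confirm with dialysis centers whether they took place; it does not ask for stenosis detail. Some first occlusions may be dated late or go unclassified.

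None of this answers Steps 1 and 2: no endpoint separates closure from assisted patency, and the stated ground for leaving obstructions out of safety fails for the reopened ones.

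**Conclusion.** The point holds as a definition and labelling problem with one internal inconsistency. Target-lesion Assisted Primary Patency as written is cumulative patency. Complete occlusions that are reopened lower neither assisted measure, so the statements in Sections 2.1, 4, 7.1 and 9 that obstructions are captured there are not true of those events. At 30 days the Index does not fill the gap.

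The direction relative to a first-occlusion measure is certain by definition. The size is unknown: zero if no occlusion is reopened and 2 points per affected subject at 50 subjects, under the assumed counts and complete follow-up used above. Primary effectiveness is untouched, because the re-intervention already counts as a loss there. For a secondary, descriptive endpoint this is a worthwhile and cheap clarification, not a threat to the study's main result.

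**What to change.** 1. In Sections 2.2 and 9, define loss of target-lesion Assisted Primary Patency as the first complete occlusion of the target lesion, whether or not it is later reopened. Date it by the adjudicated intervention or by the finding of occlusion. Interventions on a lesion that is still open do not count as a loss.
2. Keep the present uncorrectable-occlusion result beside it, labelled secondary (cumulative) patency. Likewise label the circuit measure that ends at access abandonment as cumulative.
3. Report how many re-interventions have no recorded pre-treatment stenosis.
4. Reconcile the statements in Sections 2.1, 4, 7.1 and 9 about where obstructions are captured with these definitions, and align the 30-day timepoint between Sections 2.2 and 9.

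The cost is mainly wording and one extra tabulation. Additional visits already record percent "stenosis before treatment" for any intervention done, and under Section 8 the DMC/CEC adjudicates all target lesion and access circuit interventions. The assisted figure may come out somewhat lower, and stenosis detail for revisions at other facilities will be incomplete. The 12-month window widened for COVID-19 suggests that follow-up may already be under way; keeping the present result alongside means nothing prespecified is lost.
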